Appendix B. Stage 2 Schedule of Assessments

	SCR ¹	Cycle 1			Cycle n ²				EOT or ET Visit	SFU ³ Visit	
		Day			Day						
Procedures and Treatments	-14	1	8	15	1	8	15	18-21			
Informed consent	X										
Medical and medication history	X										
Complete physical examination including weight and height	X										
ECOG performance status	X	X ⁴			X ⁴				X	X	
Pregnancy test	X ⁵	X ^{4, 6}							X		
Weight and BSA calculation (everolimus/RX-0201 arm only)		X ⁴	X ¹⁸		X ⁴	X ¹⁸					
Resting vital signs	X	X ⁴	X ¹⁸	X ¹⁸	X ^{4, 16}	X ^{16, 18}	X ^{16, 18}		X	X	
Hematology ⁷ , chemistry ⁷ , and coagulation ^{7, 16}	X	X ⁴			X ⁴				X		
Urinalysis ⁷	X	X ⁴			X ^{4, 16}				X		
Eligibility confirmation, randomization	X										
Everolimus administration ⁸		X	—————→								
Everolimus compliance ⁹			X ¹⁸	X ¹⁸	X	X ¹⁸	X ¹⁸		X		
RX-0201 infusion (everolimus/RX-0201 arm only)		X	————→		X	————→					
RX-0201 compliance (everolimus/RX-0201 arm only)			X	X		X	X		X ¹⁰		
Adverse events ¹¹ and concomitant medication ¹⁶ assessment		X	X ¹⁸	X ¹⁸	X	X ¹⁸	X ¹⁸		X	X	
Pharmacokinetic sampling				X ¹⁷							
Disease assessment(s)	X ¹							X ¹²	X ¹³		
Biomarker blood sample		X ⁴						X ¹⁴	X ¹⁴		
Archival Tumor Tissue		X ¹⁵									
Tumor biopsy (optional)		X ⁴									

Abbreviations: SCR = screening, ECOG = Eastern Cooperative Oncology Group, SFU = safety follow up visit; EOT = end of treatment visit; ET = early termination

- 1 Screening procedures will be performed within 14 days of enrollment/ randomization, except baseline tumor assessment, which can be evaluated within 21 days of enrollment/ randomization
- 2 Cycles 2 – n will follow the same assessment schedule
- 3 Safety follow-up visit will occur approximately 30 (+ 7) days after the last administration of RX-0201 or everolimus, whichever occurs later
- 4 Assessment can be performed within 5 days before Day 1 of each cycle
- 5 A serum pregnancy test must be negative for all females of childbearing potential
- 6 A urine pregnancy test must be negative for all females of childbearing potential before treatment begins. If a serum pregnancy test was done and determined negative within 72 hours of planned first dose a urine pregnancy test is not needed
- 7 See Appendix C for analytes to be collected. If screening laboratory tests were performed within 72 hours of Cycle 1 Day 1, they do not need to be repeated on Cycle 1 Day 1. Samples to be taken before any RX-0201 or everolimus is administered
- 8 Everolimus (10 mg) will be taken at the clinic on Cycle 1 Day 1, and then at home every day thereafter
- 9 Subjects will bring all everolimus packaging (empty and full) to the clinic to determine drug compliance. For subjects receiving everolimus alone, compliance will be verified at least once per cycle when the subject returns to the site.
- 10 RX-0201 compliance will be checked at the Early Termination if the subject was receiving RX-0201 at the time of early termination.
- 11 All adverse events attributed to study drug(s) will be assessed until resolution or return to baseline
- 12 Disease assessment will occur at the end of every 2 cycles
- 13 Subjects first meeting criteria for complete response or partial response at the last on-treatment tumor assessment should have a follow-up tumor assessment at the End of treatment or Early Termination visit providing it is ≥ 3 weeks from the previous tumor assessment in order to confirm the response based on RECIST ver. 1.1 criteria
- 14 Biomarker blood samples will be collected within 1 day of the disease assessment (approximately at the end of every 2 cycles and at EOT/ET if applicable)
- 15 Tissue blocks or tissue sections from initial diagnosis or upon diagnosis of advanced metastatic disease will be available for submission to the central laboratory within approximately 4 weeks after initiation of study treatment; exceptions require written documentation of why a sample is not available and prior approval by the sponsor before randomization
- 16 Cycles 1-16 only
- 17 For subjects receiving RX-0201, one blood sample will be drawn prior to the end of infusion. If the sample draw is inadvertently missed, it can be drawn on Day 15 in a subsequent cycle.
- 18 For subjects receiving everolimus alone, the assessment may be completed by phone.

Appendix C. Laboratory Analytes

Chemistry

Sodium
Potassium
Chloride
Total protein
Albumin
Calcium
Phosphorus
Glucose
BUN
Serum Creatinine
Uric acid
Total bilirubin
Amylase
Lipase
Alkaline phosphatase

AST (SGOT)
ALT (SGPT)
GGT
Creatine Kinase

Urinalysis

Specific gravity
pH
Hemoglobin
Protein
Glucose
Bilirubin
Ketones
WBC
RBC
Epithelial cells
Bacteria

Hematology

RBC
Hemoglobin
Hematocrit
MCV
MCHC
Platelets
WBC
Differential
• Eosinophils
• Basophils
• Lymphocytes
• Neutrophils

Coagulation

PT or INR
PTT

Other Labs

Urine HCG
Serum HCG
HBV*
HCV*
HIV*

ALT = alanine amino transferase; AST aspartate amino transferase; BUN = blood, urea, nitrogen; GGT = gamma-glutamyl transferase; HBV = hepatitis B virus; HCV = Hepatitis C virus; HCG = human chorionic gonadotropin; HIV = Human Immunodeficiency Virus; INR = international normalized ratio; MCV = mean corpuscular volume; MCHC = mean corpuscular hemoglobin concentration; PT = prothrombin time; PTT = partial thromboplastin time; RBC = red blood cells; WBC = white blood cells

*If a subject's HIV, HBV, or HCV status can be confirmed via medical record to be negative, new tests do not need to be performed.

Appendix D. Pharmacy Guide

RX-0201

Packaging and Formulation

RX-0201 was manufactured by Avecia Biotechnology in Milford, MA and packaged by Formatech in Andover, MA and distributed using Calent's distribution processes (Mt. Laurel, NJ) clinical study drug distribution procedures. RX-0201 will be supplied as a sterile lyophilized powder that will be reconstituted with sterile water for injection immediately prior to its administration by continuous infusion. Each 10 ml glass vial will contain 438 mg of RX-0201.

Labeling

Each vial will be labeled with the product name, study number, Sponsor name, lot number, manufacturing date, storage conditions and Investigational use statement.

Storage

The study drug, RX-0201 must be stored between --30 to -15°C. If the storage temperature is outside the range please contact Rexahn or its designee for instructions.

Records of the actual storage conditions during the period of the study must be maintained (e.g., records of the date and time and initials of person checking, and the "working day" temperatures of the room used for storage of clinical study supplies, continuous temperature recordings, or regularly maintained temperature alarm systems used in conjunction with temperature recording).

Preparation for Intravenous Administration

For each cycle of RX-0201, a total of 2 infusion bags will be used, one 1000 ml infusion bag for each of the two 7-day treatment weeks. Each infusion bag lasts approximately 7 days and will be prepared at the time of use, with a 7-day dose plus overage. In order to conserve the drug product, it is recommended that only a 10% overage be prepared. However, recognizing that individual site pharmacy policy may only allow full day doses to be administered, other overages (e.g. 1 day or ~14%) may be prepared when required. In each RX-0201 treatment cycle, the first bag will be prepared at the beginning of the infusion, Day 1, and the second bag will be prepared on Day 8. The site staff will calculate the total weekly dose for each subject based upon their BSA calculation, using either the DuBois or Mosteller formulas. The same formula for calculating BSA for a subject should be used throughout the study. The calculation will be documented in the subject's source records. If a subject's prior 2 weight measurements have varied $\leq 10\%$, the site staff may use the previous BSA calculation to expedite the drug ordering and preparation process.

RX-0201 will be administered via continuous infusion with an ambulatory infusion pump. If the pump fails, the subject will notify the site. The pump will be replaced.

The dose of infused RX-0201 in 1000 ml infusion bags will be prepared as follows on the day when administration is to begin:

1. On Days 1 and 8 of each RX-0201 cycle, calculate the body surface area (BSA) for the subject using the DuBois or Mosteller formulas. The body weight will be taken on the day of planned dosing. This BSA will be recalculated for each drug administration.

$$\text{DuBois: BSA (m}^2\text{)} = 0.20247 \times \text{Height (m)}^{0.725} \times \text{Weight (kg)}^{0.425}$$

$$\text{Mosteller: BSA (m}^2\text{)} = (\text{Height (cm)} \times \text{Weight (kg)} / 3600)^{1/2}$$

- Calculate the total weekly dose for each subject based upon the subject's BSA using the following formula which includes a 10% overage:

$$\text{Total Weekly RX-0201 Dose plus 10\% (0.7 day) overage (mg)} = \text{BSA (m}^2\text{)} \times 125 \text{ (or 200 or 250) mg/m}^2\text{/day} \times 7 \text{ days} \times \underline{1.10}$$

- Determine the number of RX-0201 vials needed for the dosing.
- Allow RX-0201 vials to equilibrate to room temperature prior to use. Vials may be thawed at 2 to 8°C for up to 24 hours and/or at room temperature for up to 2 hours prior to reconstitution.
- Reconstitute each RX-0201 vial containing 438 mg by adding 6.6 ml of sterile water for injection to prepare a concentration of 66.4 mg/ml of RX-0201. Reconstituted vials should be stored at 2 to 8°C for no longer than 4 hours.
- Calculate the volume (in ml) of drug to be added to the 1000 ml infusion bag containing normal saline for 7 days of dosing plus 10% overage using the following formula:

$$\text{Total volume of RX-0201 (ml)} = \text{Total Weekly RX-0201 Dose + overage (mg) calculated in Step 2} \text{ divided by } 100 \text{ mg/ml}$$

RX-0201 in normal saline will be infused into the subject via an intravenous access device (such as a Port-a-Cath® or PICC line) using a volumetric infusion pump with an in-line 0.2-0.22 micron sterile (disposable) filter at a rate of 5.0 ml/hour. The total volume administered over a 7-day period (168 hours) will be 840 ml. If a 10% overage is prepared, the bag will contain 924 ml.

Each bag will be prepared as follows on the day when administration is to begin:

- Commercially supplied saline bags:
 - Create a bag with a volume of 924 ml (10% overage) of normal saline. Using a commercially supplied 1000 ml bag of normal saline remove the manufacturer's overfill plus 76 ml to reduce the volume of the bag to 924 ml.
 - From the 924 ml bag, remove a volume of normal saline to equal the amount of RX-0201 diluted above in Step 5 above (Total Volume of RX-0201 + overage).
- Saline bags produced using automated on-site pharmacy systems:
 - Create a bag with a volume equal to 924 ml (10% overage) less the amount of RX-0201 diluted above in Step 5 above (Total Volume of RX-0201 + overage).
- Add the calculated volume of the reconstituted RX-0201 (100 mg/ml) to the infusion bag and mix completely (turn the bag upside down several times but do not shake vigorously).
- Remove all air from the bag before use.

When the subject returns to the site at the end of the infusion the volume and amount of RX-0201 infused will be recorded into the subject's medical record.

Supply and Return of Drug

At study initiation and as needed thereafter, RX-0201 will be shipped to a responsible person (e.g., a pharmacist) at the investigator's institution, who will check the amount and condition of the drug and enter these data into the Proof of Receipt Form and Investigational Product Accountability Record. The Proof of Receipt Form should then be sent to Rexahn or its designee and the original retained at the site. At the end of the study, or as directed, all RX-0201 supplies will be destroyed at the site or returned to Rexahn or its designee.

Investigational Product Accountability

An Investigational Product Accountability Record for the investigational products as mandated by the protocol must be kept current and should contain:

- the dates and quantities of investigational product received from Rexahn
- lot number for product received
- subject's identification (subject number and initials)
- date and quantity of investigational product dispensed (and remaining, if from individual subject drug units)

- the initials of the dispenser
- dose preparation records
- date and quantity of drug returned to the investigator/pharmacy, if appropriate

Where applicable, describe whether the returned investigational product will need to be weighed or counted.

The Return of Investigational Product for Destruction Form must be completed and included in the shipment of used and unused investigational product to Rexahn or its designee. At the end of the study, the Final Investigational Product Reconciliation Statement must be completed and provided to Rexahn.

These inventories must be made available for inspection by an authorized Rexahn representative and regulatory agency inspectors. The investigator is responsible for the accountability of all used and unused clinical study supplies.

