10. INVESTIGATIONAL PRODUCT

10.1 RX-0201

RX-0201 is a fully phosphorothioated 20-mer oligonucleotide synthesized by Avecia Biotechnology Inc, Milford, MA. The study drug was manufactured by Formatech, Andover, MA. Labeling and clinical distribution will be done by Catalent, Mt. Laurel, NJ. RX-0201 will be supplied as a sterile lyophilized powder that will be reconstituted with sterile water for injection immediately prior to its administration by continuous infusion.

RX-0201 will be provided as a lyophilized powder in 10 ml glass vials with rubber stoppers for intravenous administration. Each vial will contain 438 mg of RX-0201. The formulated RX-0201 is a lyophilized powder and is to be stored at -30° to -15°C away from light. The powder will be reconstituted using sterile water for injection prior to administration by continuous intravenous infusion. The reconstituted product should be stored at 2° to 8°C for no more than 4 hours if administration is delayed. Appropriate temperature monitoring should be maintained and recorded by the site during the study. The reconstituted drug product, diluted in 0.9% saline, is stable at 25°C to 40°C for up to 8 days.

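### Appendix D gives two incompatible concentrations for reconstituted RX-0201 (66.4 and 100 mg/ml); followed literally, its steps deliver 66.4% of the assigned dose

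*Protocol*

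**What the plan says.** Three instructions in Appendix D, under Preparation for Intravenous Administration, fix how much drug goes into each bag.

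- **Reconstitution.** Each 438 mg vial is made up by "adding 6.6 ml of sterile water for injection to prepare a concentration of 66.4 mg/ml of RX-0201".
- **Volume to draw.** The weekly dose in mg, overage included, is divided by 100 mg/ml.
- **Bag filling.** "Add the calculated volume of the reconstituted RX-0201 (100 mg/ml) to the infusion bag and mix completely".

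The vial content is consistent throughout. Protocol 10.1 says "Each vial will contain 438 mg of RX-0201", the packaging paragraph of Appendix D says "Each 10 ml glass vial will contain 438 mg of RX-0201", and the reconstitution step repeats 438 mg.

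The bag is made to 924 ml for a 10% overage, with saline removed to make room for the drug, and runs at 5.0 ml/hour, or 840 ml over seven days. Other overages are permitted: "other overages (e.g. 1 day or ~14%) may be prepared when required". Preparation happens "On Days 1 and 8 of each RX-0201 cycle".

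When the subject returns, "the volume and amount of RX-0201 infused will be recorded into" the medical record. Appendix D does not say how the amount is to be calculated. SAP 8.6 defines RX-0201 compliance as volume administered over reservoir volume. SAP 8.9 sums received doses without saying how the milligrams are obtained.

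**The concern.** The same solution cannot be both 66.4 and 100 mg/ml. If it is really 66.4, a volume calculated at 100 contains too little drug, and every bag made that way is short by the same fraction.

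The shortfall is large relative to the dose levels under study. The ratio of 100 to 66.36 is 1.51, against escalation steps of 1.60 and 1.25 in Table 1 of protocol 6.3. A subject nominally on 250 mg/m²/day would receive less than the 200 level. A subject reduced to 125, below which protocol 6.6.1 stops RX-0201, would receive 83.

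Up to 20 sites take part, and SAP 7.4 combines all centers. If some pharmacists followed the formula and others noticed the conflict and used 66.4, Stage 2 would mix two delivered doses under one nominal dose. Neither volume-based compliance nor an amount computed at 100 mg/ml would reveal it.

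**Working it through.** **Inputs** (Appendix D unless noted): 438 mg per vial; 6.6 ml diluent; stated concentration 66.4 mg/ml; divisor 100 mg/ml; overage factor 1.10; bag volume 924 ml; pump rate 5.0 ml/hour; dose levels 125, 200 and 250 mg/m²/day (protocol 6.3). Body surface area (BSA) is assumed at 1.9 m² for the example, with a range of 1.6 to 2.2 m².

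**1. The plan's own figures**
- 438 / 6.6 = 66.36, which rounds to the stated 66.4 mg/ml.
- 5.0 × 168 = 840 ml, and 840 × 1.10 = 924 ml. Both reproduce.

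**2. What 100 mg/ml would require**
- 438 / 100 = 4.38 ml final volume per vial, or 6.6 × 100 = 660 mg per vial. Neither appears in the documents.
- Volume taken up by the powder would put the true concentration below 66.36, further from 100.

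**3. Delivered fraction if the steps are followed literally**

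Delivered / assigned = [(BSA × dose × 7 × 1.10 / 100) × 66.36 × 840/924] / (BSA × dose × 7) = 66.36 / 100 = 0.664.

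BSA, dose and the overage cancel.

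| Nominal dose (mg/m²/day) | Delivered (× 0.6636) |
|---|---|
| 125 | 83.0 |
| 200 | 132.7 |
| 250 | 165.9 |

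**4. One bag: assumed BSA 1.9 m², nominal 250, 10% overage**
- Dose plus overage: 1.9 × 250 × 7 × 1.10 = 3657.5 mg.
- Volume drawn by the formula: 3657.5 / 100 = 36.6 ml, holding 2427 mg.
- Volume needed: 3657.5 / 66.36 = 55.1 ml.
- Daily dose delivered: 2427 / 924 × 120 / 1.9 = 165.9 mg/m²/day (120 ml is one day at 5.0 ml/hour).

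**5. One-day overage, assuming a 960 ml bag (840 + 120)**
- 1.9 × 250 × 8 = 3800 mg; 38.0 ml drawn, holding 2522 mg.
- 2522 / 960 × 120 / 1.9 = 165.9 mg/m²/day, the same result.

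**6. Recorded amount for a full 840 ml infusion, nominal 250, 10% overage**
- Delivered: 2427 × 840/924 = 2207 mg.
- Recorded if computed at 100 mg/ml: 3657.5 × 840/924 = 3325 mg.
- Overstatement: 1118 mg per bag, or 1.51-fold.
- At BSA 1.6 m²: 2800 − 1858 = 942 mg. At BSA 2.2 m²: 3850 − 2555 = 1295 mg.

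**The case against.** The contradiction itself is hard to dispute: 100 mg/ml appears both in a formula and in plain prose, so it is not a text-extraction fault. The best opposing case is about consequences.

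- **A pharmacist or the accountability records might catch it.** In the example, 3657.5 / 438 = 8.35, so nine vials (59.4 ml) are reconstituted but only 36.6 ml is drawn. The remaining 22.8 ml is about 3.5 vials, in a text that asks sites to conserve drug. This stands as a possible route to detection, but it is not a control. The plasma concentrations might also show the shortfall, but the plan does not use them to check preparation.
- **Nothing shows that anyone was under-dosed.** This stands. Protocol 2.3.2 reports Stage 1 complete and nine Stage 2 subjects randomized and treated by 06 March 2017, before the amendment of 8 March 2017 named in SAP 3.1. The pharmacy text in force for them is not available. With three Stage 2 subjects on everolimus alone (protocol 3.3), about six of the nine would have received RX-0201.
- **The one-day overage result depends on an assumed bag volume.** This also stands. An eight-day dose placed in a 924 ml bag would deliver 2522 / 924 × 120 / 1.9 = 172 mg/m²/day, or 69.0%. The 10% case, which Appendix D recommends, is unaffected.
- **SAP 8.9 contains no error of its own.** This is correct; it is silent on the calculation rather than wrong. The sentence proposed for it is the least essential part of the remedy.

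**Conclusion.** The concern holds. The vial content, the diluent volume and 66.4 mg/ml agree with one another; 100 mg/ml agrees with none of them. As written, Appendix D delivers 66.4% of the assigned dose, so nominal 250 becomes about 166 mg/m²/day. This assumes literal use of the steps, the 438 mg and 6.6 ml figures being correct, and a bag volume matched to the overage. It does not depend on BSA or dose level.

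This must be fixed because a dosing instruction used for every RX-0201 bag is wrong as written. Whether Stage 1 or Stage 2 subjects were under-dosed cannot be settled from these documents. For earlier bags, use of the 100 mg/ml divisor implies under-dosing only if the vials were also reconstituted to about 66.4 mg/ml.

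**What to change.** 1. Promptly tell sites to confirm the reconstituted concentration with the sponsor before preparing another bag.
2. State one verified concentration in the reconstitution step, the volume formula and the bag-filling step. It is 66.4 mg/ml if the 438 mg vial and 6.6 ml diluent are correct.
3. In parallel, check the dosing calculations required by protocol 6.1.3 and the preparation records required by Appendix D, for both the reconstituted concentration and the divisor used. If they show vials at about 66.4 mg/ml dosed with the 100 mg/ml divisor, the sponsor, medical monitor and investigators should reassess the Stage 2 dose before correction raises those subjects' exposure about 1.5-fold. DLT, PK and efficacy results should then be presented by delivered dose.
4. Preferably, add a sentence to SAP 8.9: received mg equals the recorded volume infused times the bag concentration actually prepared, not an amount derived from a nominal 100 mg/ml.

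The cost is one site notice, a correction in three places, a check of records already required, and one SAP sentence. Dose reassessment and delivered-dose tables are an added cost only if the records show the conflicting steps were followed.

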Appendix E. RECIST ver. 1.1

(Eisenhauer, E. A., et al., 2009)

Definitions

- **Measurable Disease** - the presence of at least one measurable lesion. If the measurable disease is restricted to a solitary lesion, its neoplastic nature should be confirmed by cytology/histology.
 - **Measurable Lesions** - lesions must be accurately measured in at least one dimension (longest diameter in the plane of measurement is to be recorded) with a minimum size of 10 mm by CT scan (irrespective of scanner type) and MRI (no less than double the slice thickness and a minimum of 10mm); 10mm caliper measurement by clinical exam (when superficial); or 20 mm by chest X-ray (if clearly defined and surrounded by aerated lung).
 - **Non-measurable Lesions** - all other lesions, including small lesions (longest diameter <20 mm with conventional techniques or <10 mm with spiral CT scan), ie, leptomeningeal disease, ascites, pleural/pericardial effusion, inflammatory breast disease, lymphangitic involvement of the skin or lung, and also abdominal masses/ abdominal organomegaly identified by physical exam that is not measurable by reproducible imaging techniques. Lytic bone lesions, with an identifiable soft tissue component, evaluated by CT or MRI, can be considered as measurable lesions if the soft tissue component otherwise meets the definition of measurability previously described. Blastic bone lesions are non-measurable.
- All measurements should be taken and recorded in metric notation, using a ruler or calipers. All baseline evaluations should be performed as closely as possible to the beginning of treatment and not more than 21 days before study day 1.
 - The same method of assessment and the same technique should be used to characterize each identified and reported lesion throughout the trial.
 - Clinical lesions will only be considered measurable when they are superficial (eg, skin nodules and palpable lymph nodes) and ≥ 10 mm in diameter as assessed using calipers. For the case of skin lesions, documentation by color photography, including a ruler to estimate the size of the lesion, is recommended.

Methods of Measurement

- CT is the best currently available and reproducible method to measure lesions selected for response assessment. MRI is also acceptable in certain situations (e.g. for body scans but not for lung). CT and MRI should be performed with cuts of 5 mm or less in slice thickness contiguously. When CT scans have a slice thickness >5 mm, the minimum size should be twice the slice thickness. Spiral CT should be performed using a 5 to 8 mm contiguous reconstruction algorithm. This applies to tumors of the chest, abdomen and pelvis. Head and neck tumors and those of extremities usually require specific protocols.
- Ultrasound should not be used to measure tumor lesions.
- Cytology and histology can be used to differentiate between partial response and complete response in rare cases (eg, after treatment to differentiate between residual benign lesions and residual malignant lesions in tumor types such as germ cell tumors).

Baseline Documentation of “Target” and “Non-Target” Lesions

- All measurable lesions up to a maximum of two lesions per organ and five lesions in total, representative of all involved organs should be identified as **target lesions** and recorded and measured during screening.
- It may be the case that, on occasion, the largest lesion does not lend itself to reproducible measurement in which circumstance the next largest lesion which can be measured reproducibly should be selected.
- A sum of the diameters (longest for non-nodal lesions, short axis for nodal lesions) for all target lesions will be calculated and reported as the baseline sum diameters. The baseline sum diameters will be used as reference by which to characterize any objective tumor regression in the measurable dimension of the disease. If lymph nodes are to be included in the sum, only the short axis will contribute. All other lesions (or sites of disease) should be identified as non-target lesions and should also be recorded during screening. Measurements of these lesions are not required, but the presence or absence of each should be noted throughout the study. It is possible to record multiple nontarget lesions involving the same organ as a single item on the eCRF (e.g. “multiple enlarged pelvic lymph nodes” or “multiple liver metastases”).

Subsequent Documentation of “Target” and “Non-Target” Lesions

- All target lesions (nodal and non-nodal) recorded at baseline should have their actual measurements recorded at each subsequent evaluation, even when very small (e.g. 2mm). However, if target lesions or lymph nodes become so faint on CT scan that the radiologist may not feel comfortable assigning an exact measure and may report them as being ‘too small to measure’, a default value of 5mm should be assigned
- When non-nodal lesions ‘fragment’, the longest diameters of the fragmented portions should be added together to calculate the target lesion sum. Similarly, as lesions coalesce, a plane between them may be maintained that would aid in obtaining maximal diameter measurements of each individual lesion. If the lesions have truly coalesced such that they are no longer separable, the vector of the longest diameter in this instance should be the maximal longest diameter for the ‘coalesced lesion’
- Finding of a new lesion should be unequivocal: i.e. not attributable to differences in scanning technique, change in imaging modality or findings thought to represent something other than tumor. This is particularly important when patient’s baseline lesions show PR or CR. When in doubt, subsequent timepoint should be evaluated. Lesion seen in anatomical region which was not imaged at baseline = new lesion

Response Criteria

Evaluation of Target Lesions

- * Complete Response (CR): Disappearance of all target lesions. Any pathological lymph nodes (whether target or non-target) must have reduction in short axis to <10 mm.
- * Partial Response (PR): At least a 30% decrease in the sum of the diameters of target lesions, taking as reference the baseline sum of diameters.

- * Progressive Disease (PD): At least a 20% increase in the sum of the diameters of target lesions, taking as reference the smallest sum recorded since the treatment started (nadir). The sum must also demonstrate an absolute increase of at least 5 mm over nadir.
- * Stable Disease (SD): Neither sufficient shrinkage to qualify for PR nor sufficient increase to qualify for progressive disease.

Evaluation of Non-Target Lesions

- * Complete Response (CR): Disappearance of all non-target lesions and normalization of tumor marker levels. All lymph nodes must be non-pathological in size (<10 mm short axis).
- * Non-CR/ Non-PD: Persistence of one or more non-target lesion(s) and/or maintenance of tumor marker levels above normal limits.
- * Progressive Disease (PD): Appearance of one or more new lesions and/or unequivocal progression of existing non-target lesions. Unequivocal progression of existing non-target lesions is defined as: (1) overall level of substantial worsening in non-target disease such that, even in presence of SD or PR in target disease, the overall tumor burden has increased sufficiently to merit discontinuation of therapy; or (2) in the absence of measurable disease, change in non-measurable disease is comparable in magnitude to the increase that would be required to declare PD for measurable disease. Examples include an increase in a pleural effusion from 'trace' to 'large', an increase in lymphangitic disease from localized to widespread
- Not evaluable (NE) When no imaging/measurement is done at all at a particular time point, the patient is not evaluable (NE) at that time point. If only a subset of lesion measurements are made at an assessment, usually the case is also considered NE at that time point, unless a convincing argument can be made that the contribution of the individual missing lesion(s) would not change the assigned time point response

Evaluation of Best Overall Response

The best overall response is the best response recorded from the start of the treatment until disease progression/recurrence (taking as reference for progressive disease the smallest measurements recorded since the treatment started). In general, the patient's best response assignment will depend on the achievement of both measurement and confirmation criteria

Target lesions	Non-Target lesions	New Lesions	Overall response
CR	CR	No	CR
CR	Non-CR/ non-PD	No	PR

CR	NE	No	PR
PR	Non-PD or not all evaluated	No	PR
SD	Non-PD or not all evaluated	No	SD
Not all evaluated	Non-PD	No	NE
PD	Any	Yes or No	PD
Any	PD	Yes or No	PD
Any	Any	Yes	PD

CR = Complete Response; PR = Partial Response; SD = Stable Disease; PD = Progressive Disease; NE = Not Evaluable

- Patients with a global deterioration of health status requiring discontinuation of treatment without objective evidence of disease progression at that time should be classified as having “symptomatic deterioration”. Every effort should be made to document the objective progression even after discontinuation of treatment.
- In some circumstances it may be difficult to distinguish residual disease from normal tissue. When the evaluation of complete response depends on this determination, it is recommended that the residual lesion be investigated (fine needle aspirate/biopsy) to confirm the complete response status.

Confirmation

- To be assigned a status of partial response or complete response, changes in tumor measurements must be confirmed by repeat assessments during the study.
- In the case of SD, measurements must have met the SD criteria at least once after study entry at a minimum interval (in general not less than 6 – 8 weeks) that is defined in the study protocol.

Overall Response First Timepoint	Overall Response Subsequent Timepoint	BEST overall response
CR	CR	CR
CR	PR	SD, PD, OR PR
CR	SD	SD provided minimum criteria for SD duration are met. Otherwise PD
CR	PD	SD provided minimum criteria for SD duration are met. Otherwise PD
CR	NE	SD provided minimum criteria for SD duration are met. Otherwise NE
PR	CR	PR
PR	PR	PR
PR	SD	SD

PR	PD	SD provided minimum criteria for SD duration are met. Otherwise PD
PR	NE	SD provided minimum criteria for SD duration are met. Otherwise NE
NE	NE	NE

Duration of Overall Response

- The duration of overall response is measured from the time measurement criteria are met for complete response or partial response (whichever status is recorded first) until the first date that recurrence or progressive disease is objectively documented, taking as reference for progressive disease the smallest measurements recorded since the treatment started.

Duration of Stable Disease

- SD is measured from the start of the treatment until the criteria for disease progression are met, taking as reference the smallest measurements recorded since the treatment started.
